# 3.1 Primary Objective

The primary objective of this study is to determine whether, compared to placebo treatment, administration of BCAA's, at one or more doses, after a concussion improves processing speed recovery at one or more time-periods post concussion. In the event that differences are observed, we will determine whether differences in processing speed between BCAA-treated and placebo-treated groups reflect differences in the maximum level of impairment and/or increases in the subsequent speed of improvement.

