## 7 STATISTICAL CONSIDERATIONS

### 7.1 **Primary Endpoints**

We hypothesize that neurocognitive function in concussed subjects will initially worsen and then improve in a non-linear fashion over the course of the study, and that, compared to the placebo group, one or more of the BCAA dose level groups will show a reduced nadir in cognitive performance and/or a more rapid recovery. Currently, the time course of the worsening and improvement of neurocognitive function after concussion is not well understood. Thus, part of our study will aim to identify times when maximal differences between groups may be observed. The primary analysis in this exploratory study will consider three key time periods, Days 3-6, 7-10 and 11-14 when we expect differences in processing speed between the BCAA-treated groups and placebo to be largest.

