## 7.3.2 Primary Efficacy Analysis

The primary intent to treat analysis will include all subjects who enroll and contribute at least 10 days of data to the study. The mean trajectory in decline and recovery in processing speed is unknown. Thus the primary analysis will aim to determine whether there are differences in processing speed between the BCAA dose groups and placebo, and if so, at what time periods the differences are most pronounced. The primary analysis will focus on results for the first 10 days of the study when we anticipate that the majority of subjects will be highly compliant. We will model processing speed as a function of dose and day of study and will allow differences between dose groups to vary as a function of time through a series of interaction terms. To ensure that the number of interaction terms does not become too large, we will consider groups of two to four time points, looking specifically at whether

04/06/2018 V 0.16

there are differences between any of the dose groups and placebo at Days 1-2, 3-6, 7-10, 11-14, 15-18, 19-21. The primary analysis will consider three key time periods, Days 3-6, 7-10 and 11-14 when we expect differences in processing speed between the BCAA-treated groups and placebo to be largest. Since processing speed differs with age, the model will be adjusted for age to account for any imbalances in age between dose groups. A mixed effects model will be used to account for correlations between repeated measurements on individual subjects. Likelihood ratio tests will be employed to specifically test whether there are differences in mean processing speed between placebo and any of the BCAA doses at the three key time periods. These three global tests will be conducted at a family-wise error rate of 0.05, using a Bonferroni correction to account for the three individual global tests. If statistical significance is achieved for the global test, we will then compare individual dose levels to placebo within time periods, again using a correction for four multiple tests per key time period.

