In addition to the primary analysis, this feasibility study will consider several approaches to modeling a smooth function for the trajectories of the individual processing speeds. The first model will fit non-linear curves to the trajectory of processing speed for the dose groups  $04/06/2018 \vee 0.16$ 

and then compare the mean curve for the BCAA dose groups to the placebo group, using an interaction term that allows differences between groups to vary over time. The basis for this model will be a smoothing spline. This first model assumes that the trajectories are smooth over time, albeit somewhat different between groups. We will carry out a hypothesis test of the difference between the groups using a likelihood ratio test for models with and without terms for the treatment effect and treatment by time interactions. A second model conceptualizes an initial increase in processing speed followed by a period of gradual improvement and by a transition where processing speed plateaus. This transition is of interest as we hypothesize that it represents the time when processing speed has returned to baseline. Here we anticipate a model using a quadratic with a change-point, with separate baseline functions for the dose and placebo groups and separate change-points. Correlation between repeated measurements on the same individual over time will be modeled using random effects i.e., a mixed effects model will also be used for these analyses.

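### A single quadratic running up to the change-point tends to date the plateau early when recovery slows down, so its change-point should not be reported as recovery time

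*Combined protocol and SAP*

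**What the plan says.** Section 7.3.2 plans several trajectory models in addition to the primary analysis. The first is a smoothing spline with a group-by-time interaction. The second is described by its shape: "A second model conceptualizes an initial increase in processing speed followed by a period of gradual improvement and by a transition where processing speed plateaus". Processing speed is measured in seconds, so an increase is a worsening. The form is then given: "Here we anticipate a model using a quadratic with a change-point", "with separate baseline functions for the dose and placebo groups and separate change-points". The change-point is the move to the plateau, and of that move the plan says "we hypothesize that it represents the time when processing speed has returned to baseline".

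Two other places bear on this. Section 3.1 wants any difference between groups attributed to "differences in the maximum level of impairment and/or increases in the subsequent speed of improvement". Section 7.1 hypothesises that "one or more of the BCAA dose level groups will show a reduced nadir in cognitive performance and/or a more rapid recovery".

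No equation, join condition or knot at the nadir is written down. Section 7.3.2 also concedes: "The mean trajectory in decline and recovery in processing speed is unknown".

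**The concern.** The description has three phases but only one change-point, placed between the second and third. On the natural reading, one quadratic carries both worsening and recovery. A quadratic that rises and then falls descends faster each day until it is cut off, which is the opposite of a recovery that slows into a plateau. The least-squares fit then tends to place the cut-off while a real deficit remains.

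Section 7.3.2 plans no other explicit estimate of recovery time for processing speed; the Cox model in 7.3.3 concerns return to school and sport. A plateau dated days early would misstate recovery time. If the error differs between arms, it would also blur the distinction that 3.1 asks for.

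**Working it through.** **Design inputs (7.4).** SD 0.10, intra-class correlation 0.5, three measurements per period, 10 per group, two-sided 0.05 over four contrasts. The plan gives no figure for the change-point. Its one design figure reproduces: the SD of a three-day mean is 0.10 × √((1 + 2 × 0.5)/3) = 0.0816, and the detectable difference is √(2/10) × 0.0816 × (2.498 + 0.842) = 0.122. The same inputs give the within-subject SD used for noise below: 0.10 × √0.5 = 0.0707.

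**Algebra.** Let y = a + bt + ct² up to τ, and constant after τ. A rise then a fall needs b > 0 and c < 0, with the vertex at v = −b/(2c). The slope s days after v is −2|c|s, the mirror image of s days before. Improvement is therefore fastest at τ and then stops. The curvature of worsening and recovery is tied.

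**Assumed true curves.** The plan gives none, so all are assumptions. The deficit rises linearly from d0 at Day 0 to A at day p, then recovers. The model (continuous at τ) is fitted by least squares to noise-free daily means on Days 0-21, with a grid search on τ.

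*Recovery ending on a known day T:* deficit = A(1 − (t − p)/(T − p))^k. Grid: p = 2 to 5; T = 10, 12, 14; d0 = 0, 0.03, 0.05, 0.08; A = 0.20; 48 curves per k.

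| Recovery shape | Days early: min / median / max |
|---|---|
| k = 1 (straight line) | 0.4 / 1.6 / 3.5 |
| k = 1.5 | 1.2 / 3.1 / 5.6 |
| k = 2 | 1.6 / 3.7 / 6.6 |
| k = 3 | 2.2 / 4.8 / 8.5 |

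Example: with p = 3, T = 14, k = 2 and d0 = 0.05, the fitted τ is 8.45, which is 5.55 days early. The true deficit there is 0.20 × (1 − 5.45/11)² = 0.051, a quarter of the peak.

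*Exponential recovery, half-life h, d0 = 40% of the peak.* Residual at τ = 0.5^((τ − p)/h); 90% recovery falls at p + h × log₂10.

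| Nadir day | h | Fitted τ | Deficit left at τ | Day of 90% recovery |
|---|---|---|---|---|
| 2 | 3 / 4 / 5 / 6 | 7.4 / 8.5 / 9.5 / 10.45 | 29 / 32 / 35 / 38% | 12.0 / 15.3 / 18.6 / 21.9 |
| 3 | 3 / 4 / 5 / 6 | 8.4 / 9.45 / 10.4 / 10.5 | 29 / 33 / 36 / 42% | 13.0 / 16.3 / 19.6 / 22.9 |

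**Effect of a shallower nadir on τ.**

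- Exponential, nadir 40% shallower on Day 2, h = 3/4/5/6. With both arms starting at 40% of the placebo peak, τ moves later by 1.1/2.0/2.95/3.0 days. At 20% the shift is 0.9/0.95/1.0/1.0, at 10% it is 0/0/0.95/0.05, and at 0% it is zero. The shallower arm truly reaches a given deficit h × log₂(1/0.6) = 2.2/2.9/3.7/4.4 days sooner.
- Whole deficit scaled by 0.6, including Day 0: no shift, because least-squares τ does not depend on amplitude.
- Known end day, nadir halved: median shift +0.05, +0.10 and +0.20 day at d0 = 0.03, 0.05 and 0.08; at least half a day in 7, 9 and 21 of 48 curves; largest +1.85; slightly negative in 4 of 144.
- Equal absolute linear recovery rate (true end Day 14 against 8-8.5): τ is 11.5-11.65 against 7.25-7.75, so the direction is right.
- With noise, 10 per arm, four curves: the mean shift is 0.2 to 2.3 days later, against an SD of τ of 0.9 to 4.2 days.

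**The case against.** - **The model is not fully specified.** The plan only anticipates it. With a smooth join at τ, the fitted value moved to Day 18 or later, mostly the search limit, instead of early. A jump at τ still gave an early date (8.05 for a true Day 14 in the curve tried). This objection stands as a condition on the result and is itself a reason to write the equation.
- **Subjects may be past their peak at enrolment**, which can be up to 72 hours after injury. Such curves with a true end on Day 14 gave τ = 14.0, 13.3, 14.0 and 10.5 for k = 1, 1.5, 2 and 3. This also stands as a condition, but 7.1 and 7.3.2 hypothesise worsening during the study, and the model should fit that hypothesis.
- **The model is exploratory.** It sits beside a spline and plotted daily means with intervals, which show nadir and recovery directly. No primary test or sample size uses it. This stands and limits the weight of the point.
- **A reader might infer that a shallower nadir will generally look like slower recovery, so that benefit reads as harm.** The documents do not support that. The shift needs a shared non-zero Day 0 deficit, which is plausible because treatment starts after a diagnosed concussion, but the plan does not give its size. The shift can be zero or go the right way. In several of the larger shifts (nadir Day 2, h = 4 to 6) the shallow arm's fitted initial slope is negative, so the cause there is unequal misfit and not a mirror-image arc.
- **A reader might also infer that nadir depth and recovery speed cannot be separated at all.** That is wrong. With group-specific a, b, c and τ, depth above the plateau is |c|(τ − v)² and mean recovery speed is |c|(τ − v), and these can vary independently. Only the curvature is tied.

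**Conclusion.** The concern holds in a limited form. Given one quadratic, a flat plateau without a smooth join and a peak within the study, the fitted change-point was early in every rise-then-fall curve tried. Where recovery slows to a known end day, the error is 1.2 to 8.5 days; straight-line recovery gives 0.4 to 3.5. Under exponential recovery, 29-42% of the peak deficit remains, 4.6 to 12.4 days before 90% recovery. That conflicts with reading the change-point as return to baseline.

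The effect of nadir depth is a conditional secondary risk: 0 to about 3 days later, often under half a day, and modest against the sampling spread. It can blur the distinction sought in 3.1 but does not reliably reverse it. All sizes rest on assumed trajectories. The primary period-mean tests are unaffected.

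**What to change.** In 7.3.2, write out the equation and do one of the following:

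- Give worsening its own segment with a change-point at the nadir, then a separate recovery curve to a plateau, with group-specific nadir, recovery and plateau parameters. As a check, a linear rise to a free knot followed by its own recovery quadratic and a plateau returned 13.25 to 14.0 for a true Day 14 in five noise-free curves, with the same values at peaks of 0.20 and 0.10. Those test curves are close to the fitted form, so this is a favourable test.
- Or read nadir level, and time from nadir to a set fraction of recovery, off the spline already planned, with intervals from a bootstrap by subject.

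Either way, do not report the single quadratic's change-point as recovery time.

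The cost is wording and a little more programming, with no new data. A non-linear recovery form may need starting values, or the spline as fallback, with about 10 subjects per arm.

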#### 7.3.3 Analysis of Secondary Endpoints

Secondary endpoints, including clinical symptoms such as the posturography and sleep assessments, and the learning, attention and working memory components of the neurocognitive battery will be modeled using a similar approach as described above for the primary efficacy analysis (Section 7.3.2), with the goal of assessing differences between groups over time, after adjustment for age differences. We will assess the distribution of the outcome and either use a transformation to achieve approximate normality or use a generalized mixed effects model. Time to event outcomes (e.g. time to return to school or sports participation) will be modeled using a Cox proportional hazards model. We will secondarily adjust our primary models for body mass index (BMI) and compliance to obtain information on whether individuals with lower BMI, and presumably higher BCAA/kg dosing have better outcome.

We will also monitor compliance including adherence to treatment and daily completion of neurocognitive testing. It is of interest to determine whether there are differences in compliance among the dosage groups versus placebo whether compliance decreases as a function of time, and whether compliance differs among groups over time. Adherence to treatment is measured in terms of number of bottles of consumed per day (0, 1, or 2) and will be modeled as an ordinal outcome. Adherence to treatment will be assessed using generalized estimating equations (GEE) models as we have repeated measures on adherence for each subject across all time points in the study and are primarily interested in differences between groups. In particular we anticipate that with regular prompting and encouragement, subjects will consistently complete their neurocognitive functioning tests up until about 10 to 14 days into the study. We anticipate that compliance may begin to decrease around the 10 to 14 day point as subjects begin to feel better and return to their normal routines. Assessment of compliance will be key information needed to design the anticipated pivotal trial of subsequent research studies.

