## 3.2 Secondary Objectives

The secondary objectives are to:

- Determine whether administration of BCAA's improves neurocognitive recovery compared to placebo for the cognitive domains of attention, learning, and working memory, and if so determine whether the results reflect differences in maximum levels of impairment or increases in subsequent speed of improvement.
- Evaluate whether BCAA supplementation improves clinical symptom resolution.
- Determine whether BCAA supplementation reduces the time to return to normal activities, specifically school or work, and participation in sports.
- Assess dose-related compliance of subjects with daily self-administration of BCAA's and with completion of study endpoints.
- Assess feasibility of enrolling potential subjects within 72 hours of concussion injury.
- Assess safety of BCAA supplementation in concussed patients.

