#### 6.1.2 Concussion History

- Concussion history will be obtained via interview: number of times diagnosed with a concussion and date of last concussion.
- History of current concussion obtained from the subject and family members, if necessary, via interview including: mechanism of injury, for sports-related concussions: sport and position and specific mechanism (head-to-head, head-to-ground, hit-to-body, etc), day and time of the injury, was the subject helmeted, presence and duration of loss of consciousness. The subject may bring a clinic note from their referring physician and refer to it for answers to these questions if they are unsure or sustained amnesia from their concussion. For CHOP patients, data may be collected directly from the medical record of their CHOP visits if subjects/parents are unable to provide.

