#### 6.2.3 Cognitive and Physical Activity Assessments

Subjects will be asked daily to indicate their level of cognitive and physical activity via the study website. The physical activities are based on the "Graduated Return to Play" protocol recommended in the Consensus Statement on Concussion in Sport. The cognitive activities are based on return to school guidelines used at CHOP.

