### 7.2 Secondary Endpoints

- Repeated measurements of neurocognitive functioning (CCAT test of attention, learning, and working memory) sampled over a period of 21 days.
- Clinical symptoms.
- Time to return to school/work, and sports participation.
- Tolerability of BCAA's based on AE's.
- Compliance.
- Safety and incidence of AE's and serious adverse events (SAE's).

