## 13.2 APPENDIX 2: Physical and Cognitive Activity Assessments

Please indicate your level of cognitive activity in the past day [insert date]:

1.	Cognitive Activity:	$\square_0$ Complete cognitive rest
		I Not attending school/work, but doing light cognitive activity, (e.g. watching TV, pleasure reading or using the Internet)
		□ 2 Not attending school/work, but doing moderate cognitive activity, (e.g. homework, academic reading, school/work-related computer use)
		□ 3 Attending school/work with decreased workload (e.g. not taking exams, taking a reduced number of courses)
		Full unrestricted participation in school/work including all exams, assignments, and homework

Please indicate your level of physical activity in the past day [insert date]:

2.	Physical Activity:	$\square_0$ Complete physical rest			
		$\Box_1$ Light aerobic activity (e.g. walking, swimming or stationary cycling)			
		$\square_2$ Moderate non-contact exercise (e.g. running, skating drills in hockey, running drills in soccer or football)			
shooting drills in sports, partial participation in gy classes) $\Box_4$ Complex activity or drills with full participati		$\square_3$ Complex activity or drills involving partial participation (e.g. passing or shooting drills in sports, partial participation in gym class or exercise classes)			
		$\Box_4$ Complex activity or drills with full participation (e.g. full contact practice, normal training activities, full participation in gym class or exercise classes)			
		$\square_5$ Normal activity level without limitation, including normal game or scrimmage play			

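### Return to school/work is recorded on a form with no answer for days without school or work, so subjects out of session through Day 21 cannot be told apart from subjects who have not recovered

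*Combined protocol and SAP*

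**What the plan says.** Section 3.2 sets the objective: "Determine whether BCAA supplementation reduces the time to return to normal activities, specifically school or work, and participation in sports". Section 7.2 lists the matching endpoint, "Time to return to school/work, and sports participation", and Section 7.3.3 gives the method: "Time to event outcomes (e.g. time to return to school or sports participation) will be modeled using a Cox proportional hazards model". Nothing further is said about event, origin, censoring or risk set.

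Section 6.2.3 describes the data collection: "Subjects will be asked daily to indicate their level of cognitive and physical activity via the study website". The form is Appendix 2.

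- **Cognitive item.** It asks "Please indicate your level of cognitive activity in the past day [insert date" and has five levels: total mental rest, two levels for people not at school or work (the higher one begins "Not attending school/work, but doing moderate cognitive activity"), attendance with a lighter load, and "Full unrestricted participation in school/work including all exams, assignments, and homework". There is no level for a day on which no school or work was scheduled.
- **Physical item.** It has six levels. The fifth includes full participation in gym or exercise classes, and the top one is normal, unlimited activity.

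Baseline data do not fill the gap. Section 6.1.1 records highest education attained, not whether the subject now attends school or works. Section 6.1.2 asks about sport only "for sports-related concussions: sport and position and specific mechanism". Section 4.4.1 does not require school, work or sport for entry.

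**The concern.** A time-to-return endpoint needs two things: a recorded state that means the subject is back, and a risk set of people who could be back. The cognitive item gives neither for a subject with nothing to attend. Fully recovered, that subject must choose a not-attending level or rest every day, or claim attendance that did not take place.

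The situation is likely to arise. Subjects are aged 11 to 34, outreach goes to high schools and a university campus (Section 10.5), recruitment is expected to take 12 to 18 months (Section 7.4), and follow-up is only 21 days. A summer break can cover one subject's whole follow-up.

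The daily answer cannot be recovered later. Section 7.3.2 says the study will guide dose and timing choices for later efficacy studies, so an ambiguous return endpoint could carry forward.

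**Working it through.** **The plan's own figures.** None are given for this endpoint. The only power statement (Section 7.4) concerns processing speed. It reproduces: the SD of a three-day mean is 0.10 × √((1 + 2 × 0.5)/3) = 0.0816, and the detectable difference is 0.0816 × √(2/10) × (2.498 + 0.842) = 0.122 s. It has no bearing on time to return.

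**Assumptions for the illustration (not from the documents).** Recovery times are exponential, the true hazard ratio is 2 and the placebo median m is 7 or 10 days. A share p of each arm has no school or work through Day 21, always ticks a non-attending level and stays at risk. From the plan: 21 days of follow-up and 10 subjects per arm.

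**Why the ratio shrinks.** Let S0 and S1 be the proportions not yet recovered among subjects able to return, in the placebo and active arms. The observed ratio at time t is

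2 × (S1/S0) × [p + (1 − p)S0] / [p + (1 − p)S1].

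At t = 0 this is 2. At Day 21 with m = 10 and p = 0.20, S0 = 2^(−2.1) = 0.233 and S1 = 2^(−4.2) = 0.054. The ratio is then 2 × 0.233 × (0.387/0.244) = 0.74. It drifts from 2 to below 1, so hazards are no longer proportional and the Cox model reports an average.

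**Cox estimate (large-sample simulation) and events per 20 subjects.** Events = 10(1 − p)[(1 − 2^(−21/m)) + (1 − 2^(−42/m))].

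| p | HR, m = 10 | HR, m = 7 | Events, m = 10 | Events, m = 7 |
|---|---|---|---|---|
| 0 | 2.0 | 2.0 | 17.1 | 18.6 |
| 10% | 1.75 | 1.63 | 15.4 | 16.7 |
| 20% | 1.62 | 1.48 | 13.7 | 14.9 |

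**Chance imbalance.** With Binomial(10, p) affected subjects per arm, two arms differ by 2 or more with probability 0.24 at p = 10% and 0.39 at p = 20%.

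**Weekends.** Two days in seven (29%) are weekend days. A recovery dated then is recorded 1 to 2 days late, a mean delay of about 0.43 day over all subjects. In simulation on a daily grid (m = 7), the hazard ratio was 1.95 with weekends and 1.94 without.

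**Short breaks.** A 9-day vacation starting at random for 10 to 30% of subjects left the ratio at about 1.93 to 2.01, with about 17 events per 20 subjects.

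Attenuation therefore comes only from subjects out of session for essentially the whole follow-up.

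**The case against.** Three stronger readings are tempting, and the documents do not support them.

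- **That the plan counts such subjects as not returned.** No section states an event rule or names Appendix 2 as the source. Both are inferences, though no other instrument in the schedule records return.
- **That subjects without a sport can never return to sport.** The top physical level can be ticked by anyone back to normal activity, and the level below covers gym and exercise classes. What remains is narrower: the item asks what was done in the past day, so a recovered athlete may score low on a day without sport.
- **That weekends and ordinary holidays bias the result.** They delay the recorded date in every arm and prevent nothing. Form dates identify weekends, and the sleep form (Appendix 3) invites a free-text remark on holidays.

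It is also fair to say that this is one of several secondary endpoints in a feasibility study that claims no power for it. At a true ratio of 2 with 17 events, the 95% interval is about exp(0.693 ± 1.96 × 2/√17), or 0.8 to 5.2. The noise is larger than the bias, so it would be too strong to say that the objective goes unanswered.

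One point stands against this defence. Dates and remarks do not show whether a given subject had school or work to return to, and no rule links them to the endpoint.

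**Conclusion.** The point holds for return to school/work. The form cannot separate a subject who has not recovered from one with nothing to attend, and no baseline item identifies the second group. Keeping that group at risk pulls a true hazard ratio of 2 to about 1.6 to 1.75 if 10% are affected and about 1.5 to 1.6 if 20% are.

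Those sizes rest on assumed shares, exponential recovery, placebo medians of 7 to 10 days, and affected subjects ticking a non-attending level throughout. If some instead report attendance that did not occur, the error takes another form. The real share could be smaller or larger than assumed.

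For return to sport the problem is limited to possible under-recording on days without sport. This is a worthwhile, inexpensive correction to a secondary endpoint, held with moderate confidence. It does not touch the primary analysis.

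**What to change.** 1. **Form.** Add an answer to the cognitive item for a day with no school or work scheduled, and one to the physical item for a day with no sport or exercise scheduled.
2. **Visit 1.** Before treatment starts, record whether school or work is in session over the next three weeks and whether the subject played a sport before the injury.
3. **Section 7.3.3.** Name Appendix 2 as the source. Define each event by form level, and state the origin, the censoring and the handling of days with nothing scheduled. Limit the school/work Cox model to subjects with school or work in session. Fit the return-to-sport model in all subjects and repeat it, as a sensitivity analysis, in those with a pre-injury sport.
4. **Subjects already enrolled.** Use form dates, age and the sleep-form holiday remark as proxies, under a rule written before unblinding.

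The cost is two web-form answers, two questions at Visit 1 and a few sentences of analysis text, with no change to treatment or visits. The downside is slightly fewer subjects in the time-to-event analysis and imperfect proxies for those enrolled earlier. If the form cannot be changed, item 3 is still worth doing, with the item 4 proxies standing in for in-session status.
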